6.6.7. Secondary objective: Procedure related complications

Objective

12) To describe procedure related complications

Endpoint

Procedure related complications

Definition of complication: An adverse event that results in invasive intervention. Intravenous (IV) and intramuscular (IM) drug therapies are considered as invasive treatment.

Analysis

All procedure related complications will be presented in a tabular format.

6.6.8. Secondary objective: Adverse events

Objective

Report all adverse events

Endpoint

Adverse events, including information of the seriousness, treatment needed, resolution and relevant judgment concerning the causal relationship with the investigational devices or procedure will be summarized for safety information.

Analysis

All adverse events will be presented in a tabular format.

6.6.9. Secondary objective: Adverse Device Effects

Objective

Report all adverse device effects

Endpoint

Adverse device effects, including information of the seriousness, treatment needed, resolution and relevant judgment concerning the causal relationship with the investigational devices or procedure will be summarized for safety information.

Analysis

All adverse device effects will be presented in a tabular format.

6.6.10. Secondary objective: Device Deficiencies that could have led to Serious Adverse Event

Objective

Report all device deficiencies that could have led to a serious adverse event

Endpoint

Device deficiencies that could have led to Serious Adverse Events, including any corrective actions taken during the study, if any, will be summarized for safety information.

Analysis

All device deficiency that could have led to a serious adverse device effect will be presented in tabular format.

7. DATA MANAGEMENT

Electronic Case Report Form (e-CRF) will be used to collect medical history, subjects demographics, procedure related information, protocol deviations, adverse events and device deficiencies. The e-CRF will be used for data review, data cleaning and issuing and resolving queries. This e-CRF is a web-based e-CRF

IGT systems Best Status: Final	Clinical Investigation Plan Observational clinical study with Surgical Navigation to plan, position and check instrument placement for spine surgery interventions	XCY607-130099 2016 Sep 16 Revision: 6.0 Page 33 of 46
--	---	--

which is password protected and is 21 CFR part 11 compliant. At the end of the study the data will be stored as a frozen dataset and will be retained. Workflow analysis and SUS questionnaire will be performed separately from the e-CRF.

The e-CRF data from the subjects will be key-coded (pseudonymized). The information related to the subjects (like name) is kept separately in the enrollment log at the hospital. Date and time of the procedure and date of discharge will be collected. Patient dose data will not contain any patient names or numbers. Procedure date and time will be used to link the dose data to the corresponding CRF data. Exported (image) data will be de-identified. The remaining data will be de-identified. The data will be collected and stored in a secure location.

7.1. Retention period

The investigator shall maintain the records related to this study during the investigation and for a period after the study according to national regulations (5 years)
Philips will maintain the records for a period of device End of Life (EoL) plus 15 years.

The sponsor and principal investigator shall take measures to prevent accidental or premature destruction of these documents.

8. AMENDMENTS TO THE CLINICAL INVESTIGATION PLAN AND INFORMED CONSENT

Amendment to the Clinical investigational plan and the informed consent shall be notified to, or approved by the Medical Ethics Committee (MEC) and regulatory authority. The version number and date of amendments shall be documented.

Significant changes (such as device modifications, study procedures) shall be discussed with the principal investigator prior approval. All changes will be documented with a justification and described in the latest version of the Clinical Investigation Plan.

9. DEVIATIONS FROM THE CLINICAL INVESTIGATION PLAN

The Investigator is not allowed to deviate from the Clinical Investigation Plan or to enroll subjects that do not comply with all inclusion and exclusion criteria. Under emergency circumstances, deviations from the Clinical Investigation Plan to protect the rights, safety and well-being of human subjects may proceed without prior approval of the sponsor and the MEC. Such deviations shall be documented and reported to the sponsor and the MEC as soon as possible

All deviations from the Clinical Investigation Plan will be documented with date, subject, reason, actions taken and if the deviation affects subject's rights, safety and well-being or the scientific integrity of the clinical investigation. The deviation shall be notified to the Sponsor as soon as possible via the e-CRF. Deviations will be reviewed by the sponsor and in case of serious or repetitive deviations a corrective action plan may represent a need to initiate a corrective action plan with the principal investigator. In some cases, necessitate suspension of enrollment at the site or ultimately the principal investigator will be disqualified.

10. DEVICE ACCOUNTABILITY

Access to the investigational device shall be controlled and the investigational devices shall be used only in the clinical investigation and according to the Clinical Investigation Plan.

The sponsor shall keep records to document the physical location of all investigational devices from shipment of investigational device to the Investigation site until return or disposal.

The principal investigator shall keep records documenting the receipt, installation, use, return and disposal of the investigational device, including date of receipt, identification of each investigational device, the date of use, and date on which the investigational device was returned/disposed.

11. STATEMENTS OF COMPLIANCE

This clinical Investigation shall be conducted in accordance with the clinical Investigation plan, and with the ethical principles that have their origin in the Declaration of Helsinki and all applicable regional and/or

IGT systems Best Status: Final	Clinical Investigation Plan Observational clinical study with Surgical Navigation to plan, position and check instrument placement for spine surgery interventions	XCY607-130099 2016 Sep 16 Revision: 6.0 Page 34 of 46
--	---	--

national regulations. Furthermore, in Europe this clinical Investigation shall be conducted in accordance with the International Standards ISO 14155 Clinical investigation of medical devices for human subjects – Good clinical practice and the Medical Device Directive (MDD). Furthermore all investigators will complete financial disclosures, as outlined in the 21 CFR part 54.

This clinical Investigation shall not be started prior to obtaining a favorable opinion from a Medical Ethics Committee (MEC) and Regulatory authority, if required. Any additional requirements imposed by the MEC/IRB and/or regulatory authority shall be followed.

Insurance shall be provided for the subjects participating in this clinical trial according to local law.

12. INFORMED CONSENT PROCESS

Informed consent will be obtained from every subject in writing by the Investigator or his authorized designee before the clinical Investigation is started. The subject will be informed both orally and in writing about all aspects that are relevant to the subject's decision to participate in the trial, including the trial procedures and risks and benefits of participation in the clinical investigation. Ample time should be provided for the subject to read and understand the informed consent form and to consider participation. The informed consent will include personally dated signatures of the subject and the principal investigator or an authorized designee responsible for conducting the informed consent process. A copy of the signed and dated informed consent form and any other written information will be provided to the subject.

If new information becomes available that might significantly affect the subject's future health and medical care, it shall be provided to the subjects in written form. If relevant, subject shall be asked to reconfirm their continuing informed consent in writing.

13. ADVERSE EVENT REPORTING

13.1. Definitions

Adverse Event

An Adverse Event (AE) is defined as any untoward medical occurrence, unintended disease or injury or any untoward clinical signs (including an abnormal laboratory finding) in subjects, users or other persons whether or not related to the investigational device.

NOTE 1 This definition includes events related to the investigational medical device or the comparator.

NOTE 2 This definition includes events related to the procedures involved.

NOTE 3 For users or other persons, this definition is restricted to events related to investigational medical devices.

Adverse Device Effect

An Adverse Device Effect (ADE) is defined as an adverse event related to the use of an investigational medical device. Note 1. This includes any adverse event resulting from insufficiencies or inadequacies in the instructions for use, the deployment, the implantation, the installation, the operation, or any malfunction of the investigational medical device. Note 2. This includes and any event that is a result of a use error or intentional abnormal of the investigational device.

Serious Adverse Event

A Serious Adverse Event (SAE) is an adverse event that

- a) led to death, injury or permanent impairment to a body structure or body function
- b) led to serious deterioration in the health of the subject, that either resulted in
 - 1) a life-threatening illness or injury, or
 - 2) a permanent impairment of a body structure or a body function, or
 - 3) in-patient hospitalization or prolongation of existing hospitalization, or

medical or surgical intervention to prevent life-threatening illness c) led to foetal distress, foetal death or a congenital abnormality or birth defect

NOTE Planned hospitalization for a pre-existing condition, or a procedure required by the Clinical Investigation Plan, without a serious deterioration in health, is not considered a serious adverse event.

IGT systems Best Status: Final	Clinical Investigation Plan Observational clinical study with Surgical Navigation to plan, position and check instrument placement for spine surgery interventions	XCY607-130099 2016 Sep 16 Revision: 6.0 Page 35 of 46
--	---	--

Serious Adverse Device Effect (SADE)

Adverse device effect that resulted in any of the consequences characteristic of a serious adverse event

Unanticipated Serious Adverse Device Effect

Unanticipated Serious Adverse Device Effect (USADE) is a serious adverse device effect which by its nature, incidence, severity or outcome has not been identified in the current version of the risk analysis report
NOTE Anticipated serious adverse device effect (ASADE) is an effect which by its nature, incidence, severity or outcome has been previously identified in the risk analysis report.

Device Deficiency

Inadequacy of an investigational medical device with respect to its identity, quality, durability, reliability, safety or performance. This may include malfunctions, use error, or inadequacy in the information supplied by the manufacturer.

- .

13.2. Reporting

The following are considered reportable events:

- Any SAE;
- Any Device deficiency that could have led to a SAE if
 - a) suitable action had not been taken or;
 - b) intervention had not been made or;
 - c) if circumstances had been less fortunate;
 - New findings/updates in relation to already reported events.

The sponsor will report to the Competent Authority (MPA):

- All reportable events as described above, which indicate imminent risk of death, serious injury, or serious illness and requires prompt remedial actions for other patients/subjects, users or other persons, or a new finding to it: immediately, but not later than 2 calendar days following the date of awareness of the sponsor of a new reportable event or new information in relation to an already reported event.
- Any other reportable event or a new finding/update to it: immediately, but not later than 7 calendar days following the date of awareness of the sponsor of a new reportable event or new information in relation to an already reported event.

The investigator shall document these reportable events in the e-CRF which must be provided to the sponsor immediately, but not later than 3 calendar days after the investigational study site personnel's awareness of the event.

In Appendix II: List of monitor(s) provided by the sponsor which should be contacted by the investigator in the event of a reportable event is given.

- Other adverse events shall be recorded on the adverse event forms in the e-CRF. The Sponsor and Monitor can request access to this information at any time.

The CRF will include the following information for adverse event reporting: date of the adverse event, description, actions taken, resolution, assessment of both the seriousness and the relationship to Surgical Navigation application and procedure. It will be determined if the SAE is related to the device or procedure and classified according to five different levels of casualty:

- Not related (relationship to the device or procedures);
- Unlikely (relationship with use of the device seems not relevant and/or the event can be reasonably explained by another cause);
- Possible (the relationship with the use of the device is weak but cannot be ruled out completely);
- Probable (relationship with use of the device seems relevant and/or the event cannot be reasonably explained by another cause);

IGT systems Best Status: Final	Clinical Investigation Plan Observational clinical study with Surgical Navigation to plan, position and check instrument placement for spine surgery interventions	XCY607-130099 2016 Sep 16 Revision: 6.0 Page 36 of 46
--	---	--

- Cause relationship (the serious event is associated with the device or the procedures beyond reasonable doubt).

Information collected for device deficiencies are: date of device deficiency, whether this could have led to a Serious Adverse Device Effect (SADE) if a) suitable action had not been taken or b) intervention had not been made or c) if circumstances had been less fortunate.

The investigator should report to the MEC and/or competent authority these serious adverse events and device deficiencies that might have led to a serious adverse device effect, if required by MEC or competent authority.

13.3. XXXXXXXXXXXXXXXXXXXXXXXXXXXXXXXXXXXXXXX

[Redacted]

[Redacted]

[Large Redacted Area]

13.4. Unavoidable adverse events

The following unavoidable adverse events are very common during the procedures performed in this clinical trial. Unavoidable adverse events do not need to be reported if occurred in the timeframe indicated below.

Table 6: Unavoidable adverse events

Unavoidable adverse event	Time frame
Incision pain/bruising after the intervention at point of entrance for the	2 weeks

IGT systems Best	Clinical Investigation Plan	XCY607-130099
Status: Final	Observational clinical study with Surgical Navigation to plan, position and check instrument placement for spine surgery interventions	2016 Sep 16 Revision: 6.0 Page 37 of 46

intervention	
--------------	--

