13.5. Data Monitoring Committee

Since the study will include subjects with the age of 16 years and older an independent Data Monitoring Committee (DMC/DSMB) will review all adverse events and all serious adverse events during the whole study period. The DMC/DSMB will review all adverse events that may occur after the first two subject have been treated. The DMC will provide a recommendation of continuation of the study. The third and fourth subject could be included 1 week after the first two subject have been treated with pedicle screws. The DMC/DSMB will review again and will provide a recommendation of continuation of the study. The DMC/DSMB will have regular meetings to evaluate any kind of events and provide recommendations regarding continuation of the study.

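### Section 13.4 waives reporting of incision pain and bruising for 2 weeks without excluding serious cases, which conflicts with 13.2 and with the promises to report and review all adverse events

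*Protocol*

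**What the plan says.** Section 13.4 describes a class of unavoidable events as very common in these procedures and states: "Unavoidable adverse events do not need to be reported if occurred in the timeframe indicated below". Table 6 has a single row, beginning "Incision pain/bruising after the intervention at point of entrance for the", with a time frame of 2 weeks. Nothing in the section refers to seriousness, treatment given or relation to the device.

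The other rules on the same events are:

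- Section 13.2 opens its list with "The following are considered reportable events" and puts every SAE on it, without exception. The site must provide these to the sponsor within 3 calendar days. For the rest it says: "Other adverse events shall be recorded on the adverse event forms in the e-CRF".
- Section 13.1 makes an event serious if, among other routes, it led to a serious deterioration in health that resulted in "in-patient hospitalization or prolongation of existing hospitalization".
- Sections 4.2 and 6.6.8 undertake to report all adverse events, and 6.6.9 all adverse device effects.
- Section 6.6.7 defines a complication as an adverse event leading to invasive intervention, and adds: "Intravenous (IV) and intramuscular (IM) drug therapies are considered as invasive treatment".
- Section 5.5 has the monitor ensure that all adverse events reach the sponsor.
- Section 13.5 says that the DMC "will review all adverse events and all serious adverse events during the whole study period".

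**The concern.** A site that meets a serious case of incision pain or bruising in the first 2 weeks finds two instructions. One says the event must go to the sponsor within 3 days, and the other says it need not be reported. No readable clause says which prevails.

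For non-serious cases the waiver is reasonable in itself, but it does not fit the statements elsewhere that all adverse events are reported, tabulated and reviewed. The safety results are descriptive tables from about 15 to 25 subjects, and a DMC was set up because subjects from 16 years of age are included. Readers of those tables, and the DMC, would assume that the event set is complete when the protocol allows part of it to be absent.

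**Working it through.** No sample size, power or event count is involved, so the check is a comparison of the rules.

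**Step 1. Can one event fall under both 13.2 and 13.4?** Section 13.4 applies by type of event and time. Section 13.2 applies by seriousness. The overlap is incision pain or bruising at the point of entrance, within 2 weeks, that meets the full definition in 13.1. On the prolonged-stay route this takes two conditions: a serious deterioration in health, and a prolonged hospital stay resulting from it. The overlap is narrow, but the text does not exclude it.

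**Step 2. What does reporting mean in 13.4?** The section does not say. There are two readings.

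- *Narrow reading: the reportable-events route of 13.2.* That route carries SAEs, certain device deficiencies and updates to these. Routine incision pain was never on it. The waiver could then act only on serious cases, which directly contradicts 13.2.
- *Wide reading: e-CRF recording as well.* Only this reading gives the waiver any effect on routine pain, and 4.2 and 5.5 also speak of reporting for all adverse events, not only serious ones. Exempt events may then be left out of the tables in 6.6.7 and 6.6.8 and out of what the DMC sees. The conflict with 13.2 for SAEs remains, because 13.4 still does not exclude them.

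The SAE conflict therefore holds under both readings. The possible loss from the tables and from DMC review holds only under the wide one.

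**Step 3. Timing.** Sections 5.3.3 and 13.5 allow subjects 3 and 4 to be treated from 1 week after the first two, following a DMC review. That review can therefore take place at about 7 days, inside the 14-day window. Study follow-up ends at discharge (5.3.2). If a stay is 14 days or less (an assumption, since the protocol gives no expected stay), the window covers that subject's whole observation after surgery.

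**Step 4. Link to 6.6.7.** Incision pain treated with an IV or IM drug meets the wording of the complication definition. Section 13.4 says the same event need not be reported. The protocol does not say whether it counts.

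**The case against.** The best defence is that 13.4 means routine wound pain. It speaks of events that are unavoidable and very common, and it lists only one. Infection, dehiscence and haematoma are not listed. A case that seriously harms health is hard to see as routine. This is probably the intent, but the section does not state it, and 13.2 has no cross-reference that would settle the matter. Section 13.3 is redacted and might bear on the point, although neither neighbouring section refers to it for a qualifier.

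There are also safeguards. The monitor's duty in 5.5 has no exemption, source data verification is anticipated, and length of stay is a secondary endpoint, so a prolonged stay would leave a trace. These lower the chance that a serious case goes unseen. They do not reconcile the rules, and the monitor's duty is itself one of the statements that 13.4 contradicts.

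A reader might infer three stronger points that the documents do not support:

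- *That any longer stay due to incision pain is an SAE.* It is not. Section 13.1 also requires a serious deterioration in health.
- *That 13.4 removes events from the data.* It permits omission and does not forbid reporting. Under the narrow reading, e-CRF recording is not waived at all.
- *That every case treated with IV or IM drugs must be brought back in.* Depending on how often such drugs are given for pain, which the protocol does not say, this could undo the waiver altogether.

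**Conclusion.** The point stands as an internal contradiction in a safety-reporting rule. Section 13.4 cannot be applied as written to a serious case without breaching 13.2, and it does not fit the undertakings on all adverse events in 4.2, 5.5, 6.6.8 and 13.5. The effect on the tables and on DMC review depends on the waiver covering e-CRF recording.

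The size cannot be judged from the documents, because they give no frequency of serious incision pain or bruising. A reader might take one omitted SAE as a shift of 1/25 = 4.0% to 1/15 = 6.7% of subjects, or as 1 of 2 at the first DMC review. Those figures are only the weight of a single subject in a study this small, not an estimate of under-reporting. The primary accuracy endpoint is not affected, and the secondary objectives carry no pass or fail criteria. The correction is worth making because the rule governs safety reporting and costs very little to repair.

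**What to change.** 1. In 13.4, state that the exemption covers non-serious events only. It should not apply to any event that meets the SAE definition in 13.1 or is judged related to the investigational device. Those events are reported under 13.2 and 6.6.9.
2. In the same section, state whether the exemption also covers recording in the e-CRF.
3. In 4.2, 6.6.8 and 13.5, change the scope to all adverse events other than non-serious events exempt under 13.4. Align the monitor's task in 5.5 and the matching line in the Summary.
4. State whether exempt pain treated with IV or IM drugs counts as a complication under 6.6.7. The sponsor should decide this explicitly and not re-include all such cases by default.

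The cost is a few sentences of protocol text and a small number of additional adverse event forms. If the sponsor decides under item 4 that all such treated pain counts, the number of forms could be larger.
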